3.8.3. Management strategy

Management strategies will include active monitoring and intervention (surgery, stereotactic radiosurgery (SRS), fractionated radiotherapy (fRT) or discharge from outpatient clinic care) (Figure 3). **Active monitoring** is defined as regular surveillance imaging and outpatient clinical observation. Recorded factors will include:

- Number of scans, and interval between them (months)
- For each scan: peritumoural signal intensity, venous sinus involvement and meningioma volume
- Each scan will be examined alongside its corresponding outpatient clinic appointment for any evidence of meningioma-related symptoms (motor/sensory/language/cognitive/seizure/headache/other)
- The outcome of each clinical encounter (i.e. outpatient appointment) will be recorded (resume follow-up/surgery/SRS/fRT/hospital discharge)

Intervention details; if performed, will also be recorded. These will include indication for intervention (clinical-radiological/clinical/radiological/patient preference) and time to intervention. For patients treated with clinical-radiological or clinical progression, status of meningioma-related neurological morbidity will be noted.

For surgery, the following will additionally be recorded:

- Simpson grade (as recorded by the surgeon in the operative notes) (21)
- WHO grade (classified according to the WHO system in use at the time of surgery and updated according to the WHO 2016 classification dependent on pathologists' availability (22)) and presence of any reported brain invasion (yes / no / not reported)
- Postoperative medical and surgical complications recorded at 30 days (Landriel-Ibañez Classification (Table 3) (23))
- Follow-up duration (months)
- WHO performance status pre- and postoperatively and at the last follow-up appointment.
- Recurrence on contrast-enhanced MRI during that time (yes/no) and if recurred then the time to recurrence

For SRS and fRT:

- Fractionated dose (fRT), number of fractions (fRT) and total dose (fRT /SRS)
- Early and late (≥ 3 months) toxicity (assessed by CTCAE v5.0, https://ctep.cancer.gov/protocoldevelopment/electronic_applications/ctc.htm)
- Duration of follow-up post-radiation (months)
- WHO performance status pre- and post-radiation and at the last follow-up appointment
- Progression/regrowth on contrast-enhanced MRI during that time (yes/no) and if progressed/regrew then the time to progression/regrowth

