For patients discharged from outpatient care, data sources will be checked for any readmissions/rescans thought to be attributed to the incidental meningioma within the study timeframe; date of diagnosis up to the date of data entry. Outcome following readmissions/rescans will be noted.

Grade I	Any non–life-threatening deviation from normal postoperative course, not requiring invasive treatment
Grade Ia	Complication requiring no drug treatment
Grade Ib	Complication requiring drug treatment
Grade II	Complication requiring invasive treatment such as surgical, endoscopic, or endovascular interventions
Grade IIa	Complication requiring intervention without general anaesthesia
Grade IIb	Complication requiring intervention with general anaesthesia
Grade III	Life-threatening complications requiring management in ICU
Grade IIIa	Complication involving single organ failure
Grade IIIb	Complication involving multiple organ failure
Grade IV	Complication resulting in death
Surgical Complications	Adverse events that are directly related to surgery or surgical technique
Medical Complications	Adverse events that are not directly related to surgery or surgical technique
Suffix “T” (Transient)	New neurologic deficit improving within 30 days of surgical procedure; can be added to each grade of complication
Suffix “P” (Persistent)	New neurologic deficit extending beyond 30 days of surgical procedure; can be added to each grade of complication

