Pharmacological intervention	Checkbox	Prompt entry if previous option (Postoperative surgical complications) has been ticked
Surgical intervention	Dropdown list/checkbox 
 • No • Without GA • Under GA 	Prompt entry if previous option (Postoperative surgical complications) has been ticked
ICU admission	Checkbox	Prompt entry if previous option (Postoperative surgical complications) has been ticked
Organ failure	Dropdown list/checkbox 
 • None • Single-organ • Multi-organ 	Prompt entry if previous option (Postoperative surgical complications) has been ticked. Allow one option only
Persisted with no improvement beyond 30 days?	Checkbox	Prompt entry if previous option (Postoperative surgical complications) has been ticked

Postoperative medical complications	checkbox	Required
Complication	Dropdown list/check box 
 • Myocardial infarction • Arrhythmia • Pneumonia • Pulmonary embolism • Deep venous thrombosis • Urinary tract infection • Acute kidney injury • Other 	Prompt entry if previous option (Postoperative medical complications) has been ticked Allow more than one option
Pharmacological intervention	Checkbox	Prompt entry if previous option (Postoperative medical complications) has been ticked
Surgical intervention	Dropdown list/checkbox 
 • No • Without GA • Under GA 	Prompt entry if previous option (Postoperative medical complications) has been ticked
ICU admission	Checkbox	Prompt entry if previous option (Postoperative medical complications) has been ticked
Organ failure	Dropdown list/checkbox 
 • None • Single-organ • Multi-organ 	Prompt entry if previous option (Postoperative medical complications) has been ticked. Allow one option only
Persisted with no improvement beyond 30 days?	Checkbox	Prompt entry if previous option (Postoperative medical complications) has been ticked
Postoperative WHO PS	Dropdown list/checkbox 
 • 0 • 1 • 2 • 3 • 4 • 5 (dead) 	Required. Allow one option only
Recurrence	Checkbox	Prompt entry if previous option (Postoperative WHO PS) is not 5
Scan date (at recurrence or last follow-up date if no recurrence)	DD/MM/YYYY	Prompt entry if previous option (Postoperative WHO PS) is not 5

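### The surgery page's severity items do not fully carry Table 3's criteria: non-surgical invasive treatment may be derived as Grade I, and ICU stays without organ failure have no clear grade

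*Protocol*

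**What the plan says.** For operated patients, Protocol section 3.8.3 lists "Postoperative medical and surgical complications recorded at 30 days" and names the classification set out in Table 3. The risk of complications after intervention is a secondary objective (section 2.2).

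Table 3 works as follows:
- Grade I is a non-life-threatening "deviation from normal postoperative course, not requiring invasive treatment", split into Ia and Ib by whether drugs were needed.
- Grade II is "Complication requiring invasive treatment such as surgical, endoscopic, or endovascular interventions". IIa is "Complication requiring intervention without general anaesthesia" and IIb is the same with general anaesthesia.
- Grade III is "Life-threatening complications requiring management in ICU", split into IIIa (one organ failing) and IIIb (several).

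The surgery page (Appendix 1, Section/Page 6) has one block for surgical and one for medical complications. Once a complication is ticked, each block asks for pharmacological intervention, "Surgical intervention" (*No / Without GA / Under GA*), "ICU admission" (a checkbox), organ failure (*None / Single-organ / Multi-organ*) and persistence beyond 30 days. There is no field for the grade itself, and these items carry no note to the data collector.

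**The concern.** If the grade is not entered, it must be derived, and a derived grade is only as good as the items behind it. Two of the items are worded differently from the criterion they stand for.

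The first difference sits on the border between Grade I and Grade II. Table 3 draws that border at invasive treatment of any kind; the form draws it at surgery. The same label is used in the medical block, which lists events such as myocardial infarction, pulmonary embolism and acute kidney injury. If such events are treated invasively, the procedure need not be an operation.

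The second difference is at Grade III. Table 3 requires a life-threatening complication that needs ICU management, while the form asks only whether the patient was admitted to ICU.

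At stake is the severity distribution reported under a secondary objective. A derivation rule written later can combine recorded answers, but it cannot recover what a *No* stood for.

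**Working it through.** The protocol states no figure on this point, so the check sets Table 3 beside the form.

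**Step 1. Criterion against item (same in both blocks).**

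| Table 3 criterion | Form item | Match |
|---|---|---|
| Drug treatment (Ia or Ib) | Pharmacological intervention | Yes |
| Invasive treatment, three kinds given as examples (I or II) | Surgical intervention | Narrower: names one of the three |
| General anaesthesia (IIa or IIb) | Without GA / Under GA | Yes, once the item above is answered yes |
| Life-threatening and managed in ICU (III) | ICU admission | Broader: no life-threatening condition, no stated link to the complication |
| Single or multiple organ failure (IIIa or IIIb) | Organ failure | Yes |

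**Step 2. Count the possible answers.** Per block: pharmacological 2 × surgical 3 × ICU 2 × organ failure 3 = 36 patterns.

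| ICU | Organ failure | Patterns | Grade under Table 3 |
|---|---|---|---|
| No | None | 2 × 3 = 6 | Ia, Ib, IIa or IIb |
| Yes | Single or multiple | 2 × 3 × 2 = 12 | IIIa or IIIb |
| Yes | None | 2 × 3 = 6 | Neither IIIa nor IIIb |
| No | Single or multiple | 2 × 3 × 2 = 12 | Organ-failure criterion met without ICU; no rule stated |

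The rows sum to 36. These are combinations of answers, not patients, and say nothing about frequency.

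**Step 3. Follow one event.** Take a pulmonary embolism treated by an endovascular procedure, with no ICU stay and no organ failure. Table 3 makes it Grade II. A collector who reads the label literally enters *No*. Of the 6 patterns in the first row, 2 have *No* for surgery, and they give Ia and Ib. No other severity item on the page shows that an invasive procedure took place.

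**Step 4. Scale, on assumed figures.** Let *s* be the share of true Grade II events treated endoscopically or endovascularly, all answered literally. Recorded Grade II = true Grade II × (1 − *s*). The protocol gives no value for *s*. With 25 true Grade II events:
- *s* = 10%: 25 × 0.90 = 22.5
- *s* = 30%: 25 × 0.70 = 17.5

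The missing events appear as Grade I.

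**Step 5. Several complications.** Both blocks accept more than one complication (in the medical block, "Allow more than one option"), but the severity items are asked once per block. The answers can therefore support one grade per block, not one per complication. The SRS and fRT pages settle the same question by asking for the complication with the highest toxicity grade; the surgery page gives no such instruction.

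**The case against.** The strongest reply is that the page is a build specification for database developers, not the instruction that collectors follow. Section 3.9 plans data collection guides, a video manual and an assessment that must be passed in full, and section 3.7 plans two phases of testing. The guides are not shown and may define both items. The *Without GA* option also invites a wider reading than open surgery. All of this stands: under-grading is a plausible risk, not an established error.

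A reader might infer more from the ICU item, namely that routine postoperative ICU stays become Grade III and inflate it. The protocol does not support that. No rule equates an ICU tick with Grade III. The organ failure item beneath it carries the IIIa/IIIb criterion, so a planned stay with a minor complication would show as ICU with organ failure *None* and can be told apart from IIIa and IIIb. A patient without a complication never sees the item. What remains is that ICU with *None* may mix planned stays with life-threatening events that involved no organ failure, and the form does not separate them.

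It can also be said that a derivation rule, and the choice between worst grade and grade per complication, belong in an analysis plan. That is fair for the rule. It does not answer the Grade II label, because the missing information is lost at entry.

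Finally, section 3.10 names no analysis by grade, and occurrence is captured by two required checkboxes and the lists of complication types. This limits the consequence but does not remove the mismatch with section 3.8.3.

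**Conclusion.** The point holds in a limited form. Section 3.8.3 commits to Table 3, and the items from which the grade must be derived do not fully carry its criteria. A literal answer to the surgical item turns an endoscopically or endovascularly treated Grade II event into Ia or Ib. Either block is exposed; the medical block seems the more likely place, though that is a judgement and not a figure from the protocol. ICU admission with organ failure *None* has no defined grade, so those records are ambiguous rather than wrongly Grade III.

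The size cannot be estimated from the protocol: it depends on how often complications were treated invasively without surgery and on how collectors read the label. The conclusion assumes that the unseen guides do not already define the two items. It affects severity grading under one secondary objective only. Counts of patients with a complication and the external validation of IMPACT do not change.

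**What to change.** On the surgery page, in both the surgical and the medical block:

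1. Relabel the surgical item *Invasive treatment of the complication (surgical, endoscopic or endovascular): No / Without GA / Under GA*.
2. Relabel the ICU item so that it records ICU management required because of the complication.
3. State how ICU with organ failure *None* is graded; the same rule can cover organ failure without ICU.
4. State that the worst grade per block is reported, in line with the highest-grade instruction on the radiation pages.

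The cost is two labels in each of two blocks (four in all) and one short derivation rule, with no new field and no extra data entry. If the tool is already live, the new labels do not repair records already entered. Sites would need to recheck the notes of operated patients with a complication where the surgical item is *No*, or where ICU is ticked with organ failure *None*. If the data collection guide already contains these definitions, copying them onto the page is enough for items 1 and 2.

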3.8.4. Overall outcomes

Overall outcomes by the end of the study period (discharge from outpatient care/lost to follow-up/dead/under on-going active follow-up) and follow-up durations will be recorded. Any deaths encountered during follow-up will be recorded. The medical records for patients who are discharged will also be examined for mortality data.

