Outcome	Dropdown list/check box 
 • Resume follow-up (active monitoring) • Surgery • SRS • fRT • Discharge • Lost to follow-up • Dead 	Required entry. Allow one option only Note to data collector: You will be directed to the relevant page/section dependent on the choice. If the patient died or was lost to follow-up after this interval scan, please choose one of the last two options, albeit the intention might have been to continue monitoring or intervene. If the option you choose is set to take place in the future, choose the option, save the data entered and exit the form with no further information required.
SURGERY (SECTION/PAGE 6)		
Surgery date	DD/MM/YYYY	Required entry
Indication for intervention	Dropdown list/checkbox 
 • Clinical-radiological • Clinical • Radiological • Patient preference 	Required entry. Allow one option only
Preoperative WHO PS	Dropdown list/checkbox 
 • 0 • 1 	Required entry. Allow one option only

	
 • 2 • 3 • 4 	
Preoperative comorbidities	
Check box
 
 • Hypertension - systolic > 140 or diastolic > 90 and patients on medical treatment • Previous myocardial infarction • Congestive heart failure • Peripheral vascular disease • Previous stroke/TIA - If hemiplegia present, do not check • Hemi/paraplegia • Diabetes which requires medical treatment • Diabetes with end-organ damage - if so, do not check diabetes that requires treatment • COPD/Asthma • Renal disease • Mild liver disease - Hep B/C or cirrhosis without portal hypertension • Moderate to severe liver disease - cirrhosis with portal hypertension, jaundice, ascites • Peptic ulcer disease • Cancer - excluding basal cell carcinoma • Metastatic cancer - if so, do not check cancer 	
Required entry. Allow multiple options.
 
Note to data collector: Age and comorbidities will be used to calculate the age adjusted Charlson comorbidity index. Each of these is defined in the guide provided

	
 • Rheumatic or connective tissue disease • HIV/AIDS • Skin ulcers/cellulitis • Depression • Dementia • On Warfarin 	
Simpson grade	Dropdown list/check box 
 • 1-GTR • 2-GTR • 3-GTR • 4-STR • 5-STR 	Required entry. Allow one option only

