Major axis (mm)	Free field	Prompt entry if previous option (Readmitted/rescanned during the time between discharge/loss to FU and the date of data entry) has been checked Note to data collector: In mm to 1 dp. Measure on axial T1/CT + GAD
Minor axis (mm)	Free field	Prompt entry if previous option (Readmitted/rescanned during the time between discharge/loss to FU and the date of data entry) has been checked Note to data collector: In mm to 1 dp. Perpendicular to the major axis on axial T1/CT + GAD
Cor/sag major axis (mm)	Free field	Prompt entry if previous option (Readmitted/rescanned during the time between discharge/loss to FU and the date of data entry) has been checked Note to data collector: In mm to 1 dp. Maximum height
Verdict	Dropdown list/checkbox 
 • Related 	Prompt entry if previous option (Readmitted/rescanned during the time between discharge/loss to FU and the date of data entry) has been checked. Allow one option only

	
 • Unrelated 	Note to data collector: Were the symptoms attributed to the meningioma?
Outcome	Dropdown list/Checkbox 
 • Resume follow-up (active monitoring) • Surgery • SRS • fRT • Discharge • Lost to follow-up • Dead 	Prompt entry if previous option (Readmitted/rescanned during the time between discharge/loss to FU and the date of data entry) has been checked. Allow one option only Note to data collector: You will be directed to the relevant page/section dependent on the choice. If the patient died or was lost to follow-up after this interval scan, please choose one of the last two options, albeit the intention might have been to continue monitoring or intervene. If the option you choose is set to take place in the future, choose the option, save the data entered and exit the form with no further information required.
Overall outcome	Dropdown list/Checkbox: 
 • Dead • Alive 	Prompt entry if previous option (Rescanned during the time between discharge/loss to FU and the date of data entry) is not ticked. Allow one option only Note to data collector: You will be directed to section 10 if Dead is selected.
Mortality (SECTION/PAGE 10)		
Date of death	DD/MM/YYYY	Required entry

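### Appendix 1 states no route from the surgery, SRS and fRT pages to the date and cause of death, and its 30-day persistence item is narrower than suffix P in Table 3

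*Protocol*

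**What the plan says.** Section 3.8.4 commits the study without exception for treated patients: "Any deaths encountered during follow-up will be recorded". Section 3.5.2 makes death unrelated to the meningioma a secondary endpoint, and section 2.2 lists the risk of complications after surgery, SRS or fRT among the secondary objectives.

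For surgery, section 3.8.3 asks for "Postoperative medical and surgical complications recorded at 30 days", graded by Table 3. There, Grade IV is "Complication resulting in death" and suffix P is "New neurologic deficit extending beyond 30 days of surgical procedure; can be added to each grade of complication". Suffix T is given to a new deficit that improves inside the same 30 days.

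Appendix 1 puts date and cause of death in Section 10 only. The one explicit instruction leading there is attached to the overall-outcome field in Section 9, the page for discharged or lost patients: "You will be directed to section 10 if Dead is selected". The surgery page asks, for surgical and again for medical complications, "Persisted with no improvement beyond 30 days".

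**The concern.** Appendix 1 is what the database developers work from. If they follow it, a patient sent to Section 6, 7 or 8 stays there: those pages have no outcome field and no link to the mortality page. Treated patients are exactly the group in whom the complication objective is studied, and death is the most serious complication. Without date and cause, a death cannot be placed inside or outside the 30-day window, attributed to the procedure, or classed as related or unrelated to the meningioma.

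The persistence item raises a smaller, separate problem. It does not ask what Table 3 asks, so the P suffix built from it may not mean what the report will say it means.

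**Working it through.** The Protocol gives no figure to reproduce, so the check is a trace of the form.

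**Routes to date and cause of death (Appendix 1)**

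1. Section 9, overall outcome: explicit link to Section 10.
2. Management decision (Section 4), scan outcome (Section 5) and rescan outcome (Section 9): Dead is an option, with a general note that the choice directs the user to the relevant page. Each field takes one answer, and surgery, SRS and fRT are alternatives to Dead. A patient sent to Sections 6 to 8 from such a field is not also sent to Section 10 by it.
3. Sections 6, 7 and 8: no outcome field, and no stated link to Section 9 or 10.

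**What the treatment pages record when a patient dies**

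- *Early death after surgery:* postoperative performance status 5. The field has no time point, and choosing 5 suppresses the recurrence, scan-date and last-status fields. Fact of death only.
- *Later death after surgery:* the status at recurrence or last follow-up offers 0 to 4. No code.
- *Death after SRS or fRT:* the corresponding field does offer 5, beside a scan or last-follow-up date, which is not a date of death. No cause.

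The surgery page and the two radiation pages therefore differ on whether a late death can be coded, and none of the three leads to its date or cause.

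**Consequence for Table 3**

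Grades I to III depend on drug treatment, invasive treatment with or without general anaesthesia, ICU admission and organ failure. The surgery page has a field for each, so these grades can be derived. Grade IV needs a death caused by a complication, within the 30-day recording window. The page supports only an inference: status 5 together with a ticked complication.

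**Persistence item against suffixes T and P**

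- *Deficit gone by day 30:* T; box unticked. Consistent.
- *Deficit unchanged beyond day 30:* P; box ticked. Consistent.
- *Deficit partly improved by day 30 but still present afterwards:* meets both T and P in Table 3; box unticked. Ambiguous, because the two definitions overlap.
- *Deficit that first improves after day 30:* P only; the box may be left unticked because there was improvement. Clear mismatch.

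The item opens whenever any surgical complication is ticked, not when the separate box for new or worse neurological impairment is ticked. It is repeated for medical complications, where no neurological field is listed. A tick may therefore describe a lasting problem that is not a neurological deficit.

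**Competing-risk analyses (section 3.10.1)**

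In one analysis primary intervention is the event. In the other, intervention before progression is a competing event. A death after intervention changes neither.

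**Number affected**

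This is the number treated times the proportion who die by data entry. The Protocol gives neither.

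**The case against.** The strongest reply is that Appendix 1 guides the developers of a tool that section 3.7 puts through two test phases before it goes live. Section 10 exists, section 3.8.4 states the intent, and the working database may contain the link. That limits the claim: the text shows that no route is stated, not that the finished database cannot hold these deaths. It does not remove the point, because the guide is the specification and it conflicts with section 3.8.4.

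Four stronger readings are tempting, and the Protocol does not support them.

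- *That Table 3 grades will be wrong.* Suffixes T and P are added to a grade and do not set it. Only Grade IV and the suffix are in question.
- *That every partly improved, lasting deficit is misclassified.* If improvement began within 30 days, T also fits, and leaving the box unticked is defensible. The fault there lies in the overlap within Table 3. Asking the item for medical complications is not wrong in itself either, since the suffix may be added to any grade.
- *That sites are told to enter the death instead of the treatment.* The scan-outcome note says "If the patient died or was lost to follow-up after this interval scan, please choose one of the last two options", but goes on to speak of what had been intended. It most naturally covers patients who died before the intended treatment took place.
- *That the gaps make intervention look safer.* Missing late deaths could do so, but an undated status 5 without cause could equally charge an unrelated or later death to surgery. The direction is not known.

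It is also fair that post-intervention mortality is not a named endpoint.

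**Conclusion.** The point stands in limited form. As specified, date and cause of death have no stated route in any treated patient, and a late death after surgery has no code. This conflicts with section 3.8.4, leaves the cause needed for the section 3.5.2 endpoint uncollected in treated patients, and makes 30-day Grade IV an inference. The persistence item is narrower than "New neurologic deficit extending beyond 30 days of surgical procedure", with a clear mismatch only for deficits that first improve after day 30.

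The effect falls on the secondary complication objective and on cause-specific mortality after treatment. Grades I to III and both competing-risk analyses are untouched, and no effect on the primary validation is shown. The size cannot be given in patients. The conclusion assumes that the database follows Appendix 1 as written. It should be corrected before data collection, since it decides what can be reported on harm after treatment.

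**What to change.** 1. On Sections 6, 7 and 8, add a required vital status at last contact (alive or dead). Dead leads to Section 10, with one further item: did the death result from a complication of the intervention (yes or no)?
2. Add code 5 (dead) to the surgery page's performance status at recurrence or last follow-up, as the SRS and fRT pages already have.
3. Reconcile suffixes T and P in Table 3 so that a deficit partly improved by day 30 but still present belongs to one only. Then word the persistence item to match, and open it only when new or worse neurological impairment is ticked. If the suffix is to be available for medical complications, add that tick box there too.

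The cost is a few REDCap fields and one branching rule, completed from records the sites already review. Under section 3.6 the central database holds no identifiers and only the sites hold the link file, so a later repair would mean each centre going back to its notes.
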